4.3 Exclusion Criteria

Any of the following criteria will exclude patients from study participation:

EGFRm NSCLC Disease Characteristics

- 1. Documented evidence of an exon 20 insertion mutation in the EGFR gene;
- 2. Symptomatic, untreated or unstable central nervous system or leptomeningeal metastases. (Patients with treated and stable brain metastases [confirmed by 2 scans at least 4 weeks apart], with no evidence of cavitation or hemorrhage in the brain lesion are eligible provided that they are asymptomatic and do not require corticosteroids);

Medical/Surgical History

- 3. Previous treatment with rociletinib or MPDL3280A, or other 3rd generation EGFR TKI (eg, AZD-9291, HM61713), or PD-1 axis-targeted therapy (eg, anti-PD-1 or anti-PD-L1);
- 4. Prior treatment with CD137 agonists or other immune checkpoint blockade therapies, including anti-CTLA-4 therapeutic antibodies;
- 5. Uncontrolled pleural effusion, pericardial effusion or ascites requiring recurrent drainage procedures (once monthly or more frequently);
- Uncontrolled hypercalcemia (> 1.5 mmol/L ionized calcium or Ca > 12 mg/dL or corrected calcium > ULN) or symptomatic hypercalcemia requiring continued use of bisphosphonate therapy or denosumab:
 - Patients who are receiving bisphosphonate therapy or denosumab specifically to prevent skeletal events and who do not have a history of clinically significant hypercalcemina are eligible;
 - Patients who are receiving denosumab prior to enrollment must be willing and eligible to receive a bisphosphonate instead while on study.
- 7. History of severe allergic, anaphylactic, or other hypersensitivity reactions to chimeric humanized antibodies or fusion proteins;
- 8. Known hypersensitivity to Chinese hamster ovary cell products or any component of the MPDL3280A or rociletinib formulations;

- 9. History of prior allogeneic hematopoietic stem cell transplantation or prior solid organ transplantation;
- 10. History of autoimmune disease (*please review* Appendix E):
 - Patients with a history of Type 1 diabetes on a stable anti-hyperglycemic regimen; autoimmune-related hypothyroidism on a stable dose of thyroid replacement hormone; vitiligo; or alopecia are eligible for this study.
- 11. Positive test for human immunodeficiency virus (HIV);
- 12. Patients with active hepatitis B virus (HBV) (defined by a positive hepatitis B surface antigen [HBsAg] test at screening):
 - Patients with past or resolved HBV infection (defined by a negative HBsAg test and a positive anti-hepatitis B core antigen [anti-HBc] antibody test) are eligible. HBV DNA must be obtained in these patients prior to first day of study treatment.
- 13. Patients with active hepatitis C virus (HCV):
 - Patients positive for HCV antibody are eligible only if PCR is negative for HCV RNA.
- 14. Active tuberculosis;
- 15. Signs or symptoms of infection within 2 weeks prior to first day of study treatment;
- 16. Received therapeutic oral or IV antibiotics within 2 weeks prior to first day of study treatment:
 - Patients receiving prophylactic antibiotics (eg, to prevent a urinary tract infection or chronic obstructive pulmonary disease exacerbation) are eligible.
- 17. Administration of a live, attenuated vaccine within 4 weeks before first day of study treatment or anticipation that such a live attenuated vaccine will be required during the study:
 - Influenza vaccination should be given during influenza season only (approximately October to March). Patients must not receive live, attenuated influenza vaccine (eg, FluMist[®]) within 4 weeks prior to first day of study treatment or at any time during the study.
- 18. Class II to IV heart failure as defined by the New York Heart Association functional classification system (Appendix G):
 - Patients with a known left ventricular ejection fraction (LVEF) < 40% will be excluded;
 - Patients with known coronary artery disease, congestive heart failure not meeting the above criteria, or LVEF < 50% must be on a stable medical regimen that is optimized in the opinion of the treating physician, in consultation with a cardiologist if appropriate, to be eligible.
- 19. Patients who have experienced untreated and/or uncontrolled cardiovascular conditions and/or have symptomatic cardiac dysfunction (unstable angina, congestive heart failure,

myocardial infarction within the previous 3 months; coronary angioplasty, or stenting or bypass grafting within the past 6 months; cardiac ventricular arrhythmias requiring medication; any history of 2nd or 3rd degree atrioventricular conduction defects);

20. Any of the following cardiac abnormalities or history:

- Clinically significant abnormal 12-lead ECG or QT interval corrected using Fridericia's method (QT_cF) > 450 ms;
- Inability to measure QT interval on ECG;
- Personal or family history of long QT syndrome;
- Implantable pacemaker or implantable cardioverter defibrillator;
- Resting bradycardia < 55 beats/min.
- 21. History of idiopathic pulmonary fibrosis, organizing pneumonia (eg, bronchiolitis obliterans), drug-induced pneumonitis, idiopathic pneumonitis, or evidence of active pneumonitis on screening chest computerized tomography (CT) scan:
 - History of radiation pneumonitis in the radiation field (fibrosis) is permitted.
- 22. Females who are pregnant or breastfeeding;
- 23. Presence of active gastrointestinal (GI) disease (including GI bleeding or ulceration) or other condition that could affect GI absorption (eg, malabsorption syndrome, history of biliary tract disease);
- 24. Uncontrolled medical, psychological, familial, sociological, or geographical conditions that interfere with the patient's safety, ability to provide informed consent, or ability to comply with the protocol;
- 25. Malignancies other than NSCLC within 5 years prior to enrollment, with the exception of those with a negligible risk of metastasis or death (such as adequately treated carcinoma *in situ* of the cervix, basal or squamous cell skin cancer, localized prostate cancer, or ductal carcinoma *in situ*);

Previous and Concomitant Medications

- 26. Patients who are currently receiving treatment with any medications that have the potential to prolong the QT interval if that treatment cannot be either discontinued or switched to a different medication prior to first day of study treatment. The wash out period for the medication should be at least 5 times the medication's half-life (see http://crediblemeds.org/ for a list of QT-prolonging medications);
- 27. Treatment with systemic immunostimulatory agents (including but not limited to interferon [IFN], interleukin [IL]-2) within 6 weeks or five half-lives of the drug, whichever is shorter, prior to first day of study treatment;

- 28. Treatment with systemic immunosuppressive medications (including but not limited to prednisone, cyclophosphamide, azathioprine, methotrexate, thalidomide, and antitumor necrosis factor [anti-TNF] agents) within 2 weeks prior to first day of study treatment:
 - The use of inhaled corticosteroids and mineralocorticoids (eg, fludrocortisone) is allowed.

4.4 Patients or Partners of Patients of Reproductive Potential

Pregnancy is an exclusion criterion and females of childbearing potential must not be considering getting pregnant during the study. Female patients who are more than 2 years postmenopausal or have had a hysterectomy will not be considered of childbearing potential. Female patients of childbearing potential must have a negative serum pregnancy within 7 days prior to administration of the first dose of either study drug. If the serum pregnancy results are not available on first day of study treatment (Day of Run-in-Period for Phase 1; C1D1 for Phase 2), a urine pregnancy test can be performed on the first day of study treatment to confirm that the patient is not pregnant before dosing. Both values should be entered in the electronic case report form (eCRF). Another serum pregnancy test will be performed at the End of Treatment (EOT) Visit.

Women of childbearing potential must practice double-barrier methods of contraception during treatment and for 90 days after the last dose of either study drug. Adequate contraception is defined as double-barrier protection (ie, condom plus spermicide in combination with a diaphragm, cervical/vault cap, or intrauterine device). Birth control pills, birth control patches and/or injections of hormones to prevent pregnancy are not considered an adequate method of preventing pregnancy.

Men with a female partner of childbearing potential must have either had a prior vasectomy or agree to double-barrier methods of contraception during treatment and for 21 days after the last dose of either study drug to allow for clearance of any altered sperm.

Patients will be instructed to notify the Investigator if pregnancy of a female patient or a partner of a male patient is discovered to have occurred either during the patient's treatment or within 90 days (female patients) or 21 days (partners of male patients) after completion of treatment with rociletinib and MPDL3280A.

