 - Lesions that are intended to be used to collect tissue samples for biopsy should not be counted as target lesions.
- 8. Biopsy of tumor tissue for central evaluation within 60 days prior to the first day of study treatment (Run-in-Period Day 1 for Phase 1; C1D1 for Phase 2);
- 9. For Phase 1 and Phase 2 Group B, patients must have progressed after at least 12 weeks of treatment with a 1st or 2nd generation EGFR TKI (eg, erlotinib, gefitinib, afatinib) for advanced or metastatic NSCLC. A minimum of a 3-day washout period is required for previous EGFR TKIs.
 - Previous chemotherapy for NSCLC is allowed for patients enrolled in Phase 1 and Phase 2 Group B.
- 10. For Phase 2 Group A, patients must be EGFR TKI treatment-naïve and chemotherapy-naïve;
- 11. Anticipated life expectancy of at least 3 months;

Medical/Surgical History

- 12. A minimum of 14 days must have elapsed since any palliative radiotherapy;
- 13. A minimum of 14 days must have elapsed from last invasive surgery, and wound healing has occurred;
- 14. Any ongoing potentially reversible treatment-related toxicities must be resolved to Grade ≤ 1 EXCEPT alopecia or (with agreement from the Medical Monitor) the expected EGFR TKI toxicities of rash or diarrhea that are stable with intervention;
- 15. No planned major surgery while on study;

Concomitant Medications or Procedures

- 16. Women of childbearing potential must have a negative serum pregnancy test within 7 days prior to the first dose of study treatment and agree to use highly effective contraception as defined in the full protocol, during the study and for 90 days following the last dose of MPDL3280A or rociletinib;
- 17. Men with a female partner of childbearing potential must have either had a prior vasectomy or agree to use effective contraception as described in the full protocol for at least 14 days prior to administration of the first dose of study treatment, during the study, and for 90 days following the last dose of MPDL3280A or rociletinib.

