4.5 Waivers of Inclusion/Exclusion Criteria

No waivers of protocol-specified inclusion or exclusion criteria will be granted by the Investigator, the Sponsor, or its designee for any patient enrolling into the study.

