8.3 Follow-Up Period

During the Follow-Up-Period, all patients will be contacted by the site every 12 weeks $(\pm 1 \text{ week})$ for the collection of information on all subsequent anticancer therapy and for the monitoring of survival status until the patient's death, patient withdrawal of consent, or a decision by the Sponsor to cease data collection and close the study, whichever comes first. These assessments may be performed during routine clinic visits or by telephone contact.

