9.5 Pregnancy or Drug Exposure During Pregnancy

If a patient becomes pregnant during the study, the Investigator is to stop dosing with study drug(s) immediately.

A pregnancy is not considered to be an AE or SAE; however, it must be reported to the Sponsor using the Pregnancy Report Form within the same timelines as an SAE (Section 9.9). This applies to female patients as well as female partners of male patients.

A pregnancy should be followed through to outcome, whenever possible. Once the outcome of the pregnancy is known, the Pregnancy Outcome Report Form should be completed and reported to the Sponsor.

AEs or SAEs that occur during pregnancy will be assessed and processed according to the AE or SAE processes using the appropriate AE or SAE forms.

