9.9 Regulatory Aspects of SAE Reporting

All SAEs, regardless of relationship to study drug, must be reported to the safety contract research organization (CRO) within 24 hours of knowledge of the event, according to the procedures below. It is important that the Investigator provide an assessment of relationship of the SAE to study treatment at the time of the initial report. The Clinical Trial Serious Adverse Event Report Form must be used for reporting SAEs.

While not considered an SAE, pregnancy occurring in a female patient or in the female partner of a male patient must also be reported to the CRO as soon as the event is known by the clinical site. If the pregnancy occurs in a female patient, study drug should be stopped immediately. Notification to the CRO should take place via facsimile or email utilizing the Pregnancy Report Form.

Further details on SAE/pregnancy reporting can be found in the Investigator's file.

The Sponsor or its designee is responsible for submitting reports of AEs associated with the use of the drug that are both serious and unexpected to the US Food and Drug Administration (FDA), according to 21 Code of Federal Regulations (CFR) 312.32; to the Japanese Pharmaceuticals and Medical Devices Agency; to the European regulatory authorities according to the European Commission Clinical Trials Directive (2001/20/EC); and to other regulatory authorities, according to national law and/or local regulations. All investigators participating in ongoing clinical studies with the study medication will receive copies of these reports for prompt submission to their IRB or IEC. In accordance with the European Commission Clinical Trials Directive (2001/20/EC), the Sponsor or its designee will notify the relevant ethics committees in concerned member states of applicable suspected unexpected serious adverse reactions (SUSARs) as individual notifications or through periodic line listings. The Sponsor or its designee will submit all safety updates and periodic reports to the regulatory authorities as required by applicable regulatory requirements.

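### Section 4.4 asks men for 21 days of contraception after the last dose, while inclusion criterion 17 asks the same men for 90

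*Combined protocol and SAP*

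**What the plan says.** Criterion 17 appears in the same terms in the Synopsis and in Section 4.2. It applies to men with a female partner of childbearing potential who have not had a vasectomy, and its post-treatment period is 90 days from the last dose of MPDL3280A or rociletinib. Criterion 16, the matching condition for women, runs "during the study and for 90 days following the last dose of MPDL3280A or rociletinib", so both sexes have the same end point at entry. Section 4.5 makes these conditions firm: "No waivers of protocol-specified inclusion or exclusion criteria will be granted by the Investigator, the Sponsor, or its designee for any patient".

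Section 4.4 sets out the contraception rules in detail. Women are again given 90 days. Men, with the same vasectomy exception, must "agree to double-barrier methods of contraception during treatment and for 21 days after the last dose of either study drug", and the stated purpose is "to allow for clearance of any altered sperm".

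Section 4.4 also tells patients which pregnancies to notify: those found to have occurred during treatment or, afterwards, within 90 days for female patients "or 21 days (partners of male patients) after completion of treatment" with both drugs.

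The site's own reporting duty has no day limit. Section 9.5 requires pregnancies to be reported to the sponsor and adds: "This applies to female patients as well as female partners of male patients". Section 9.9 says that a pregnancy "in the female partner of a male patient must also be reported to the CRO as soon as the event is known" by the site.

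**The concern.** Two operative parts of the protocol give different durations for the same obligation in the same men. Criterion 17 refers the reader to the full protocol for the description of contraception. That description is in Section 4.4, so staff who follow the reference arrive at the 21-day sentence. The reference cannot be read as adopting 21 days, because criterion 17 states its own period.

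What is at stake is a partner-protection instruction. Two sites could advise identical patients differently, and each could cite the protocol. The notification instruction follows the shorter period, so the man is not asked to tell the site about a partner pregnancy that first occurs late in the period he agreed to at entry.

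**Working it through.** The plan gives no derived figure to reproduce, so the check is a comparison of the texts and a subtraction.

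**Step 1: are the two rules about the same thing?**

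| | Criterion 17 (Synopsis, Section 4.2) | Section 4.4 |
|---|---|---|
| Who | Men with a partner of childbearing potential | Same |
| Exception | Prior vasectomy | Same |
| Clock starts | Last dose of MPDL3280A or rociletinib | Last dose of either drug |
| Period after last dose | 90 days | 21 days |
| Status | Current text | Current text |

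No difference of phase, group or drug separates them. For women the period is 90 days in both places, so only the male period disagrees.

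**Step 2: size of the conflict.** 90 − 21 = 69 days, that is, days 22 to 90.

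**Step 3: where it would show in practice.** Section 8.2.2 schedules the End-of-Treatment visit 28 days (+7) after the last dose, or sooner if another anticancer agent is started. At a day-28 visit, Section 4.4 says that the man's obligation ended 28 − 21 = 7 days ago. Criterion 17 says that 90 − 28 = 62 days remain.

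**Step 4: the notification instruction.** The 21 days limit when the pregnancy occurs, not when it is discovered or reported. A pregnancy that occurs on day 15 and is discovered on day 60 is still notifiable. A pregnancy that first occurs on day 40 is not covered by the instruction, although it falls within the 90 days. This clock runs from completion of both drugs. Section 5.7.4 lets one drug continue after the other stops, so the two clocks coincide only if the contraception period is counted from the drug stopped later.

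**Step 5: could the site learn of such a pregnancy another way?**
- The contacts every 12 weeks in Section 8.3 are "for the collection of information on all subsequent anticancer therapy and for the monitoring of survival status".
- Tables 1 and 2 add a visit 120 days (± 30) after the last MPDL3280A dose, so at the earliest on day 120 − 30 = 90. It is for PK and anti-therapeutic antibody samples, which are taken only from patients who received MPDL3280A.

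Neither contact specifies a pregnancy question. Either could bring a pregnancy to light, and Sections 9.5 and 9.9 would then require the site to report it.

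**The case against.** The strongest reply is that the two texts can be obeyed together. Ninety days includes 21, criterion 17 binds at entry, and no waiver is allowed. Every such man has therefore had to agree to the longer period, and a site that applies it breaches nothing. This stands, and it limits the point: the texts conflict as statements of duration, but compliance with both is possible.

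A reader might infer more than the documents support, in four ways:
- **That men will in fact stop early.** No section describes counselling from Section 4.4 that replaces the agreement given at entry. The documents support only the conditional statement about a site that follows Section 4.4 alone.
- **That partners or pregnancies would be harmed.** The documents give no data on risk through sperm, and Section 1.1 reports no genotoxic activity for rociletinib in two in vitro assays.
- **That partner pregnancies after day 21 go unreported.** The site's duty has no day limit, and the 120-day visit gives most men a further face-to-face contact. The gap is in what the patient is asked to volunteer.
- **That 90 days is the intended period.** Section 4.4 gives a reason for 21 days, and criterion 17 gives none for 90. The protocol treats MPDL3280A as relevant well beyond 21 days: Section 7.7 keeps certain therapies excluded for 10 weeks after its last dose, and sampling runs to about day 120. That is a reason to ask for a justification of 21 days for that drug. It does not show a reproductive risk.

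**Conclusion.** The point holds as an internal inconsistency between two current instructions: 69 days for non-vasectomised men with a partner of childbearing potential, with a matching shortfall in the partner-pregnancy notification instruction. It is worth correcting because it concerns the protection of partners and sits in operative text. It does not threaten the trial's validity, and no endpoint, population or analysis is affected.

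The 69 days assume that both contraception periods are counted from the last dose of whichever drug is stopped later. The documents do not say which duration the sponsor intends, and the consent form was not available for this review, so what patients are actually told is unknown.

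**What to change.** In Section 4.4, change 21 to 90 days in both places: the male contraception period and the partner-pregnancy notification window. Then check that the consent form says the same. This aligns Section 4.4 with what these men must already accept at entry and with the period for women.

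If the sponsor intends 21 days, it should justify that period for both rociletinib and MPDL3280A and amend criterion 17 in the Synopsis and in Section 4.2.

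The first option changes two sentences. Its only burden is a longer contraception and notification period for men than Section 4.4 now states.

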4.5 Waivers of Inclusion/Exclusion Criteria

No waivers of protocol-specified inclusion or exclusion criteria will be granted by the Investigator, the Sponsor, or its designee for any patient enrolling into the study.

5 DESCRIPTIONS OF STUDY TREATMENT AND DOSE MODIFICATIONS

5.1 Description of Rociletinib

Rociletinib is provided as yellow, film-coated tablets for PO administration in two dosage strengths made from the same drug blend. The strengths are achieved by adjusting the total tablet weight. The strengths are differentiated by tablet shapes: 125 mg strength is a round tablet and 250 mg strength tablet is an oval tablet. Each tablet consists of rociletinib HBr drug substance, silicified microcrystalline cellulose, croscarmellose sodium, colloidal silicon dioxide, copovidone, magnesium stearate and hypromellose based film coat. Excipients used are generally regarded as safe. Tablets are packaged along with desiccant in high density polyethylene bottles closed with a child-resistant cap. Tablets will be supplied to the study sites by the Sponsor. Rociletinib tablets should be stored in their original packaging at 15°C to 30°C (59-86°F).

Child-resistant bottles containing rociletinib tablets are labeled according to applicable regulations for investigational products. Patients should be advised not to split or crush tablets. Additionally, patients should be advised not to take tablets with chips or other gross visual defects. Defective tablets should be returned to the study site.

